5.4.4 PHYSICAL EXAMINATION

A physical examination will be performed at Screening and End of Study (Day 17).

5.4.5 VITAL SIGNS

Vital signs will include the measurement of supine and standing blood pressure and heart rate, respiration rate, and body temperature. Weight and height will be measured at Screening only.

Vital signs, including supine and standing blood pressure and heart rate, temperature and respiration rate will be collected at the following visits/time points:

- Screening,
- Day -1, 7, and 14 upon clinic check-in,
- Day 1, 2, 3, 8, 9, 10, 15, 16, and 17 prior to and 4 hours post AM dosing.

5.4.6 12-LEAD ELECTROCARDIOGRAM

Twelve-lead ECG recording will be collected at Screening and End of Study (Day 17).

5.5 CONCOMITANT MEDICATIONS

The use of any concomitant medication taken during the study, including any medication taken for the treatment of AEs, will be recorded in the case report form (CRF). Recording of a concomitant medication will include the medication name, indication, dose, route, frequency, date started and date stopped.

5.6 SCREENING ASSESSMENTS

5.6.1 EPWORTH SLEEPINESS SCALE

The Epworth Sleepiness Scale (ESS) will be used to exclude subjects who demonstrated excessive sleepiness prior to randomization.

The ESS is an 8-item self-administered questionnaire to measure general level of daytime sleepiness. The Scale is based on questions referring to situations that vary in their likelihood to induce a person to fall asleep. Subjects are asked to rate how likely they would be to doze off or fall asleep in each situation in contrast to feeling just tired based on their usual way of life in recent times. Each item (or situation such as sitting and reading) is rated on a 4-point Likert scale that ranges from “0 = Would never doze” to “3 = High chance of dozing.” The total score on the Scale is the sum of the responses to each of the 8 items; therefore, the range of possible scores for each responder is 0 to 24. A total score of <10 indicates that the patient is not suffering from excessive daytime sleepiness. Individual items are not analyzed and have no independent, valid interpretations.

Subjects will complete the ESS at Screening.

6 STATISTICAL ANALYSES

All programming and analyses will be performed using SAS software v9.4.

6.1 STATISTICAL METHODOLOGY

6.1.1 DETERMINATION OF SAMPLE SIZE

This study is designed to test non-inferiority (NI) of tolperisone doses relative to placebo, with a cyclobenzaprine test versus placebo to confirm the sensitivity of the simulator to detect treatment effects. The following assumptions were made in the sample size computation: (a) within-subject standard deviation for SDLP is approximately 6 cm; (b) the true difference between tolperisone doses and placebo is 0; and, (c) the NI margin is proposed to be 4.4 cm, which is the effect seen with 0.05% of blood alcohol content (BAC) with this driving simulator scenario. Under these assumptions, a sample of 30 subjects would provide in excess of 90% power to establish NI of tolperisone compared to placebo on any given dosing day in terms of the primary end point, SDLP. This sample size is considered more than adequate to detect cyclobenzaprine differences from placebo, which are anticipated to exceed the NI margin.

6.1.2 ANALYSIS POPULATIONS

6.1.2.1 SAFETY POPULATION

The Safety Population includes all subjects who received at least 1 dose of study drug, according to the treatment received in any given treatment period.

6.1.2.2 INTENT-TO-TREAT (ITT) POPULATION

The Intent-to-Treat (ITT) Population includes all randomized subjects who receive at least 1 dose of study drug, according to the planned treatment in a given treatment period. This is the analysis population for efficacy analysis. Subjects will (in general) be included in all analyses for which data are non-missing.

6.1.2.3 PHARMACOKINETIC (PK) POPULATION

The Pharmacokinetic (PK) Population includes all subjects with evaluable plasma concentration data.

6.1.3 STATISTICAL ANALYSES – GENERAL CONSIDERATIONS

In general, categorical variables will be summarized by the count (N) and percentage of subjects (%). Continuous variables will be summarized by the number of non-missing observations (N), mean, standard deviation (SD), median, minimum, and maximum values.

Formal statistical tests (where performed) will be two-sided and testing at the $\alpha=0.05$ level of significance.

All study data are to be displayed in the data listings.

6.1.4 MULTIPLE COMPARISONS

There are a number of comparisons of interest from which conclusions with respect to the NI of tolperisone vs. placebo will result. Initially, the statistical significance of the cyclobenzaprine vs. placebo ($p<0.05$) comparison is necessary to validate the experiment as having the ability to detect effects (i.e., assay sensitivity).

Subsequently, the NI of tolperisone to placebo (for initial dose, next day residual, and steady-state dose comparisons) will result in a conclusion of NI of tolperisone relative to placebo. For NI conclusions, the alternative hypothesis (of NI) will be considered established if the upper 95% confidence limit for tolperisone vs placebo difference is less than the pre-specified NI margin of 4.4 cm.

Cyclobenzaprine comparisons to placebo are to assess assay sensitivity and no adjustment to alpha levels will be made for either the comparison of

cyclobenzaprine to placebo or tolperisone, or for secondary endpoints or analyses.

The sequence of testing to control for multiplicity associated with comparisons of tolperisone to placebo (to assess NI) on multiple days is Day 1 (single-dose), followed by Day 3 (steady-state), followed by Day 2 (residual effect). Tolperisone will be considered NI to placebo if prior comparisons (at time points in the sequence provided, above) also indicate NI.

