13 STATISTICAL METHODS

13.1 Determination of Sample Size

This study is designed to test non-inferiority of tolperisone doses relative to placebo, with a cyclobenzaprine test versus placebo to confirm the sensitivity of the simulator to detect treatment effects. The following assumptions were made in the sample size computation: (a) within-subject standard deviation for SDLP is approximately 6 cm; (b) the true difference between tolperisone doses and placebo is 0; and, (c) the non-inferiority (NI) margin is proposed to be 4.4 cm, which is the effect seen with 0.05% of BAC with this driving simulator scenario. Under these assumptions, a sample of 30 subjects would provide in excess of 90% power to establish non-inferiority of tolperisone compared to placebo on any given dosing day in terms of the primary end point, SDLP. This sample size is considered more than adequate to detect cyclobenzaprine differences from placebo, which are anticipated to exceed the NI margin.

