13.3 Statistical Analysis – General Considerations

This section describes the general approaches planned to analyze the data from this study. Additional details of the planned analyses outlined here, will be further described in the SAP.

Doses of tolperisone will be considered non-inferior to placebo if the upper 95% confidence limit on the difference in SDLP between that dose and placebo is less than 4.4 cm (the NI margin). Cyclobenzaprine comparisons to placebo are to assess assay sensitivity and no adjustment to

alpha levels will be made for either the comparison of cyclobenzaprine to placebo or tolperisone, or for secondary endpoints or analyses. Formal statistical tests (where performed) will be two-sided and testing at the $\alpha=0.05$ level of significance.

The sequence of testing to control for multiplicity associated with comparisons of tolperisone to placebo (to assess NI) on multiple days is Day 1 (single-dose) , followed by Day 3 (steady-state), followed by Day 2 (residual effect). Tolperisone will be considered NI to placebo if prior comparisons (at time points in the sequence provided, above) also indicate non-inferiorty.

In general, categorical variables will be summarized by the count (N) and percentage of subjects (%). Continuous variables will be summarized by the number of non-missing observations (N), mean, standard deviation (SD), median, minimum, and maximum values.

All study data are to be displayed in the data listings.

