6.5 PHARMACODYNAMIC ANALYSES

6.5.1 PRIMARY ANALYSIS

The primary endpoint, SDLP, will be analyzed using a mixed model repeated measures with fixed effects for sequence, period, and treatment, with repeated observations for subjects. An unstructured covariance structure and Kenward-Roger degrees of freedom will be used. In the event an unstructured covariance structure fails to converge, a variance components covariance structure will be assumed.

In addition to assessments of treatment effect, p-values for significance testing of period and sequence effects will be provided.

Pair-wise comparisons (hypothesis tests) of differences in least squares means, and 95% confidence intervals on differences will be provided (Table 14.2.1.1) for:

Initial dose effect

1. cyclobenzaprine versus placebo following Day 1 PM dose
2. tolperisone versus placebo following Day 1 PM dose
3. tolperisone versus cyclobenzaprine following Day 1 PM dose

Next day residual dose effect

4. cyclobenzaprine versus placebo following Day 2 AM dose
5. tolperisone versus placebo following Day 2 AM dose
6. tolperisone versus cyclobenzaprine following Day 2 AM dose

Steady-state dose effect

7. cyclobenzaprine versus placebo following Day 3 AM dose
8. tolperisone versus placebo following Day 3 AM dose
9. tolperisone versus cyclobenzaprine following Day 3 AM dose

In addition, pair-wise within-subject differences in SDLP greater than 4.4 cm in absolute value (equal to the previously found difference between placebo and 0.05% Blood Alcohol Content (BAC) for the CRCDS) will be compared using McNemar's test. Pair-wise, within subject differences in SDLP will also be tested for symmetry about zero (Laska 2012) using the maximally selected McNemar test (Table 14.2.1.2.1-14.2.1.2.9).

Summary statistics for raw values and change from baseline will be provided (mean, SD, median, minimum, maximum) for SDLP for each time point and treatment group. Figures will be provided for the within subject difference scores by treatment and day as both a histogram and scatter plot.

Data listings for driving simulator data will be provided (Listing 16.2.6.1.1-16.2.6.1.X).

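### Does SAP 6.1.4 need to say which day's cyclobenzaprine result establishes assay sensitivity before non-inferiority is concluded?

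*SAP*

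**What the plan says.** SAP 6.1.4 opens its decision rule with the positive control: "Initially, the statistical significance of the cyclobenzaprine vs. placebo" contrast, at p<0.05, comes first, and that "comparison is necessary to validate the experiment as having the ability to detect effects (i.e., assay sensitivity"). NI of tolperisone to placebo is taken up after that. It is judged by the upper 95% confidence limit against 4.4 cm and tested in the order Day 1, Day 3, Day 2.

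SAP 6.5.1 lists three contrasts that could serve as the control test:

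- item 1: "cyclobenzaprine versus placebo following Day 1 PM dose"
- item 4: "cyclobenzaprine versus placebo following Day 2 AM dose"
- item 7: "cyclobenzaprine versus placebo following Day 3 AM dose"

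All tests are two-sided at 0.05 (SAP 6.1.3), and the control contrasts carry no alpha adjustment.

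The protocol states the purpose of the control but attaches no condition to it. Section 13.1 describes a design "with a cyclobenzaprine test versus placebo to confirm the sensitivity of the simulator to detect treatment effects". Section 13.3 repeats that purpose and leaves the significance level uncorrected, in the sentence that begins "Cyclobenzaprine comparisons to placebo are to assess assay sensitivity and no adjustment to". It gives the NI rule on its own, with 4.4 cm as the limit, in the sentence that begins "Doses of tolperisone will be considered non-inferior to placebo if the upper 95% confidence limit on the difference in SDLP". Both sample-size sections expect the cyclobenzaprine effect to be larger than the NI margin.

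**The concern.** A condition that must hold before any NI claim should be unambiguous before the data are seen. Here it is singular while the plan has three candidates. One named day, any day, all days, or the same day as each NI test could each be argued from the text. If the control passed on some days and not on others, the rule could be chosen with the three p-values in view.

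The three drives also follow different exposures: after the second dose, before dosing the next morning, and after the Day 3 morning dose. The label in Protocol Appendix 1 reports about four-fold accumulation at steady state, so a mixed result is conceivable.

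Two further points look open. The test is two-sided with no stated direction, and no sentence says what a failed control does to the NI sequence.

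**Working it through.** **Inputs from the documents.** 30 completers, three periods, six sequences; SD 6 cm, called within-subject; margin 4.4 cm; true tolperisone difference 0; two-sided 0.05; sequence Day 1, 3, 2; control effect expected above 4.4 cm (SAP 6.1.1, 6.1.3, 6.1.4; Protocol 9.3, 13.1).

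**Assumptions not in the documents.** Between-day correlation 0 to 0.8; a per-day model with subject, period and treatment, so residual df = 90 − 1 − 29 − 2 − 2 = 56. A control pass means SDLP is higher on cyclobenzaprine with two-sided p<0.05.

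**Step 1: the plan's own figure.** Power ≈ Φ(4.4/SE − 1.960).

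- 6 cm as SD of the paired difference: SE = 6/√30 = 1.095; 4.4/1.095 = 4.017; Φ(2.057) = 0.980 (0.977 by noncentral t, 56 df). This agrees with the stated power above 90%.
- 6 cm as literal within-subject SD: SE = 6√(2/30) = 1.549; 4.4/1.549 = 2.840; Φ(0.880) = 0.811 (0.797 by t). This does not reach 90%.

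A control effect of exactly 4.4 cm has the same standardised size, so one control comparison passes with probability 0.977 or 0.797.

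**Step 2: how far apart the readings can be.** The widest contrast is any-day against all-days. Take SD of difference 6, effect 4.4 cm and independent days. All three pass with probability 0.977³ = 0.933; at least one passes with 1 − 0.023³ ≈ 1.000. The gap is 0.067. An NI claim also needs Day 1 NI, so the claims differ in about 0.067 × 0.977 = 0.065 of trials. Simulation of the full crossover (40,000 runs per setting) gives 0.066, and with correlated days:

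| Control effect, all days | SD of difference 6 | Within-subject SD 6 |
|---|---|---|
| 4.4 cm | 3.9-6.6% | 19.5-40.3% |
| 6 cm | about 0.1% | 5-8% |

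At 5 cm with SD of difference 6, the figure is 1.2-1.7%.

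**Step 3: effect following exposure.** Assume one compartment, immediate absorption and effect proportional to concentration. With 4.4 cm on Day 3 and the label's 18 h half-life, the effects on Days 1/2/3 are 2.46/2.34/4.4 cm. Over half-lives of 8 to 37 h, any-day and all-days claims then differ in 50-80% of trials (SD of difference 6) or 47-67% (within-subject SD 6). This scenario puts Days 1 and 2 at 1.8-3.8 cm, below the effect the documents expect. Keep the 18 h shape but set the lowest day to 4.4 cm: the factor is 4.4/2.34 = 1.88, giving about 4.6/4.4/8.3 cm. Disagreement falls to 3-4%, or 24-29% on the literal SD reading. A Day 3 rule and an any-day rule then differ in under 0.1% of trials.

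**Step 4: what each candidate rule costs.** Chance of NI on all three days, true difference 0, 4.4 cm control effect on all days:

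| Rule | SD of difference 6 | Within-subject SD 6 |
|---|---|---|
| Any day | 0.93-0.95 | 0.50-0.59 |
| Day 3 only | 0.91-0.93 | 0.38-0.50 |
| Same day as each NI test | 0.87-0.91 | 0.22-0.41 |

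Against this, if cyclobenzaprine were inert, an any-day rule would pass falsely with probability up to 1 − 0.95³ = 0.143 two-sided, or 1 − 0.975³ = 0.073 in the impairing direction. One named day in the impairing direction gives 0.025.

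**Step 5: direction and consequence.** With control effects of 1.8 to 6 cm, a significant result in the wrong direction on any day occurs in about 0.14% of trials or fewer. On consequence, SAP 6.1.4 places the control first, calls it necessary, and takes up NI afterwards. A failed control therefore leaves no basis for an NI conclusion.

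**The case for a change.** The best case for changing the plan is that no passage names a day and that both documents call 6 cm a within-subject SD. On that reading the any-day and all-days rules part company in 19-40% of trials at 4.4 cm. A sentence added before unblinding would need no new data, and an any-day version would cost no power relative to the most lenient reading.

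Part of this stands. The day is not stated, and a colleague drafting the SAP afresh would probably name one. The 19-40% figure is correct arithmetic, but it depends on an SD reading under which the trial does not have its stated power. That is a separate question about the sample size. It also needs a control effect at the floor of what is expected.

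The remedy is less neutral than it looks. Nothing in the documents singles out Day 3, and Protocol 13.3 and SAP 6.1.4 assign the cyclobenzaprine comparisons, in the plural, to assay sensitivity. A Day 3 rule lowers the chance of NI on all three days by about 2 points, or 8-12 on the literal SD reading. An any-day rule gives the control three unadjusted chances. A same-day rule could fail on Day 2 because little residual impairment remains, rather than because the simulator is insensitive.

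Concern about choosing the rule after the fact is also limited. The study is double-blind, and the shell of Table 14.2.1.1 prints the control and NI contrasts together for each day. A reader of the report would see any mixed result.

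**Conclusion.** No change to the plan is called for. What remains is a missing detail, the day or days that define assay sensitivity, in a rule whose purpose and consequence can be read from the text and whose contrasts are all pre-specified and displayed. Where the control passes on all three days or on none, every reading gives the same answer.

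Under the planning assumptions (30 completers, tolperisone difference 0, 6 cm as the SD of the paired difference, control effect of at least 4.4 cm on every day), the most divergent readings disagree in at most about 7% of trials, falling to about 0.1% at 6 cm. This rests on assumed between-day correlations of 0 to 0.8. It would not hold if 6 cm is truly within-subject or if cyclobenzaprine impairs driving by less than the documents expect. The choice of rule is then a trade-off between power and protection against an inert control, and the documents do not make one answer correct.

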6.1.5 PROCEDURES FOR HANDLING MISSING DATA

Subjects who discontinue, will only contribute to the pair-wise comparisons for which they have data.

For subjects that have incomplete data within an assessment, data will be listed but not summarized and/or analyzed for that assessment.

6.2 SCREENING AND BASELINE CHARACTERISTICS

Summary tables will be constructed for the following screening or baseline data: demographic characteristics of age, sex, ethnic origin, height, weight and BMI for the safety population (Table 14.1.3), reason for screen failures (Table 14.1.4), medical history (Table 14.1.7), prior medications (Table 14.3.8.1), laboratory examinations (Tables 14.3.3.1-14.3.5.2), vital signs (Tables 14.3.6.1-14.3.6.5.3), and physical examination abnormalities (Table 14.3.8.1).

Data listings will be provided for the following screening and baseline data: screen failures (Listing 16.2.2.3), inclusion/exclusion criteria (Listing 16.2.3.2.1), inclusion/exclusion criteria violations (Listing 16.2.3.2.2), characteristics of age, sex, race, ethnicity (Listing 16.2.4.1), substance use (Listing 16.2.4.2), medical history (Listing 16.2.4.3), simulator sickness questionnaire (Listing 16.2.4.4), ESS (Listing 16.2.4.5), pharmacokinetic sampling (Listing 16.2.5.2), driving simulator (Listings 16.2.6.1.1-16.2.6.1.X), AEs (Listing 16.2.7.1) laboratory collections (Listing 16.2.8.1-16.2.8.3, urine drug screen, alcohol screen, and pregnancy test (Listing 16.2.8.4), prior medication (Listing 16.2.8.6.1), physical examination (Listing 16.2.8.7), 12-lead ECG (Listings 16.2.8.8.1 and 16.2.8.8.2), and vital signs, height, weight, and BMI (Listing 16.2.8.9).

6.3 SUBJECT DISPOSITION

The number of subjects in each study population group will be presented by sequence (Table 14.1.1). The number of subjects randomized, completing each visit, discontinuing at each visit, and completing the study will be presented by

sequence (Table 14.1.2). A listing for study populations will be presented by subject (Listing 16.2.2.1).

For subjects discontinuing, individual subject information will be listed (Listing 16.2.1 respectively).

An important protocol deviation listing will be provided by subject (Listing 16.2.2.2). Deviations will be summarized category of deviation (Table 14.1.6).

Subjects excluded from the pharmacodynamics analyses will be listed (Listing 16.2.3.1).

6.4 STUDY MEDICATION ADMINISTRATION

Study drug administration data will be listed by subject (Listing 16.2.5.1). The number of days exposed for each of the three treatment populations will be summarized (Table 14.1.5).

6.5 PHARMACODYNAMIC ANALYSES

6.5.1 PRIMARY ANALYSIS

The primary endpoint, SDLP, will be analyzed using a mixed model repeated measures with fixed effects for sequence, period, and treatment, with repeated observations for subjects. An unstructured covariance structure and Kenward-Roger degrees of freedom will be used. In the event an unstructured covariance structure fails to converge, a variance components covariance structure will be assumed.

In addition to assessments of treatment effect, p-values for significance testing of period and sequence effects will be provided.

Pair-wise comparisons (hypothesis tests) of differences in least squares means, and 95% confidence intervals on differences will be provided (Table 14.2.1.1) for:

Initial dose effect

1. cyclobenzaprine versus placebo following Day 1 PM dose
2. tolperisone versus placebo following Day 1 PM dose
3. tolperisone versus cyclobenzaprine following Day 1 PM dose

Next day residual dose effect

4. cyclobenzaprine versus placebo following Day 2 AM dose
5. tolperisone versus placebo following Day 2 AM dose
6. tolperisone versus cyclobenzaprine following Day 2 AM dose

Steady-state dose effect

7. cyclobenzaprine versus placebo following Day 3 AM dose
8. tolperisone versus placebo following Day 3 AM dose
9. tolperisone versus cyclobenzaprine following Day 3 AM dose

In addition, pair-wise within-subject differences in SDLP greater than 4.4 cm in absolute value (equal to the previously found difference between placebo and 0.05% Blood Alcohol Content (BAC) for the CRCDS) will be compared using McNemar's test. Pair-wise, within subject differences in SDLP will also be tested for symmetry about zero (Laska 2012) using the maximally selected McNemar test (Table 14.2.1.2.1-14.2.1.2.9).

Summary statistics for raw values and change from baseline will be provided (mean, SD, median, minimum, maximum) for SDLP for each time point and treatment group. Figures will be provided for the within subject difference scores by treatment and day as both a histogram and scatter plot.

Data listings for driving simulator data will be provided (Listing 16.2.6.1.1-16.2.6.1.X).

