13.6 Pharmacodynamic Analyses

The primary endpoint, SDLP, will be analyzed using a normal theory mixed effects model with fixed effects for sequence, period, and treatment, and a random effect for subject within sequence. An unstructured covariance structure and Kenward-Roger degrees of freedom will be used.

Pair-wise comparisons (hypothesis tests) of differences in least squares means, and 95% confidence intervals on differences will be provided for:

Initial dose effect

1. cyclobenzaprine versus placebo following Day 1 PM dose
2. tolperisone versus placebo following Day 1 PM dose
3. tolperisone versus cyclobenzaprine following Day 1 PM dose

Next day residual dose effect

4. cyclobenzaprine versus placebo following Day 2 AM dose
5. tolperisone versus placebo following Day 2 AM dose

6. tolperisone versus cyclobenzaprine following Day 2 AM dose

Steady-state dose effect

7. cyclobenzaprine versus placebo following Day 3 AM dose

8. tolperisone versus placebo following Day 3 AM dose

9. tolperisone versus cyclobenzaprine following Day 3 AM dose

In addition, pair-wise within-subject differences in SDLP greater than 4.4 cm in absolute value (equal to the previously found difference between placebo and 0.05% Blood Alcohol Content (BAC) for the CRCDS) will be compared using McNemar's test. These pair-wise, within subject differences in SDLP will also be tested for symmetry about zero [6] using the maximally selected McNemar test.

Summary statistics will be provided (mean, SD, median, minimum, maximum) for SDLP for each time point and treatment group.

Additional details of analysis for secondary endpoints of VAS, SDC, KSS, and driving performance endpoints will be specified in the SAP.

The relationship between tolperisone plasma drug levels and driving performance (i.e., the primary endpoint of SDLP) will be assessed by correlational analyses.

All pharmacodynamic results will be summarized in tabular format, with summary statistics (number [n], mean, SD, median, minimum, and maximum) and change from baseline, as appropriate by time point.

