6.5.2 SECONDARY ANALYSES

Secondary endpoints of VAS, SDC, and driving performance endpoints will be evaluated and presented similarly, however Lane Exceedance will be log transformed (more specifically $\ln(x+1)$) prior to analyses.

Tables will be presented in the same format as the primary output:

- VAS for motivation (Table 14.2.2.1)
- VAS for self-appraisal of driving performance (Table 14.2.2.2)
- Symbol Digit Coding:
 - Number of correct responses (Table 14.2.3.1)
 - Accuracy (Table 14.2.3.2)
 - Standard deviation of reaction time (Table 14.2.3.3)
- Other Driving Performance Endpoints
 - Lane exceedance; including number, maximum, and duration (Tables 14.2.4.1-14.2.4.3)
 - Average speed, speed deviation, excessive speeding count, speeding ratio (Tables 14.2.5.1-14.2.5.4)
 - Excessive Ay and Total Collisions(cornering speed threshold exceeded) (Table 14.2.6)

-
- Divided Attention (DA): Correct Responses, Omission Errors, Commission Errors, Reaction Time, Standard Deviation of Reaction Time (Tables 14.2.8.1-14.2.8.5)
 - KSS (Table 14.2.9)

A data listing for KSS will be provided (Listing 16.2.6.2). A data listing for SDC will be provided (Listing 16.2.6.3). A data listing for the two VAS results will be provided (Listing 16.2.6.4).

Additional Secondary Analyses:

Total Collisions:

Summary statistics will be provided (mean, SD, median, minimum, maximum) for total number of collisions for each time point and treatment group (Table 14.2.7). Additionally, differences in number of collisions for each pair-wise comparison will be provided with their corresponding Wilcoxon Signed Rank p-value. A bar chart will be provided pooling total number of collisions by 0, 1, 2, or ≥ 3 for all 3 treatment groups.

Self-reported readiness

Pair-wise comparisons for readiness to drive will be analyzed using McNemar's test (Table 14.2.10).

Plasma drug levels

Blood samples for the determination of plasma tolperisone concentrations will be drawn prior to each AM dosing on Days 1-3 and post-driving test (15-30 minutes after the drive) on Days 1 and 3. The relationship between initial dose effect, next day residual dose effect, and steady-state dose effect plasma drug levels and driving performance (i.e. the primary endpoint of SDLP) will be assessed by correlation. Both the Spearman and Pearson correlations will be reported (Tables 14.2.11.2-14.2.11.22).

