Source Data: Listing 16.2.5.1

Table 14.1.6
Protocol Deviations
(Safety Population)

Deviation Category	Overall (N=xx) n (%)
xxxx	xx (xx.xx)
yyyy	xx (xx.xx)

SAS Program Name:

Date:

Source Data: Listing 16.2.2.2

Neurana 115

Table 14.1.7
Medical History
(Safety Population)

Category	Overall	
	(N=xx)	
	n	%
HEENT	xx	(xx.x)
etc	xx	(xx.x)

Subjects with more than one occurrence in a category are only counted once.

SAS Program Name:

Date:

Source Data: Listing 16.2.4.3

Table 14.2.1.1
Standard Deviation of Lateral Position (SDLP)
(ITT Population)

Day		Placebo (N=xx)	Tolperisone 450 mg (N=xx)	Cyclobenzaprine 30 mg (N=xx)
Day X	N	xx	xx	xx
	Mean (SD)	xx.xxxx (xx.xx)	xx.xxxx (xx.xx)	xx.xxxx (xx.xx)
	Median	xx.x	xx.x	xx.x
	Min, Max	xx.xxxx , xx.xxxx	xx.xxxx , xx.xxxx	xx.xxxx , xx.xxxx
		Model Fixed Effects of Interest	Tolperisone 450 mg vs PBO	Cyclobenzaprine vs PBO
	Diff in LSMean		xx.xxxx	xx.xxxx
	95%CI*		(xx.xx , xx.xx)	(xx.xx , xx.xx)
	p-value Treatment*		0.xxxx	0.xxxx
	p-value Sequence*	0.xxxx		
	p-value Period*	0.xxxx		
				Tolperisone 450 mg vs Cyclobenzaprine
				xx.xxxx
				(xx.xx , xx.xx)
				0.xxxx

Repeat table for VAS, SDC, KSS, and other driving performance measures (see SAP for proposed table list).

Mixed model repeated measures with fixed effects for sequence, period, and treatment, repeated assessments for subjects, unstructured covariance structure, and Kenward-Roger degrees of freedom.

SAS Program Name:

Date:

Source Data: Listing 16.2.6.1.X

Table 14.2.1.2.1
Standard Deviation of Lateral Position (SDLP) Analysis of Symmetry about Zero
(ITT Population - Cyclobenzaprine 30 mg versus Placebo)

Threshold	Sign	Low	Neutral	High	McNemar	Nominal P-value
x.xxxx	-/+	xx	xx	xx	x.xxxx	0.xxxxx
x.xxxx	-/+	xx	xx	xx	x.xxxx	0.xxxxx

Repeat for each comparison

SAS Program Name:

Date:

Source Data: Listing 16.2.6.1.X

Table 14.2.7
Driving Performance Total Collisions
(ITT Population)

Day	Statistic	Placebo (N=xx)	Tolperisone 450 mg (N=xx)	Cyclobenzaprine 30 mg (N=xx)
Day 1	N	xx	xx	xx
	Mean	x.x	x.x	x.x
	SD	x.xx	x.xx	x.xx
	Median	x.x	x.x	x.x
	Min, Max	xx, xx	xx, xx	xx, xx
	Diff in # of Collisions		Tolperisone 450 vs PBO	Cyclobenzaprine 30 mg
	N		xx	xx
	Mean		x.x	x.x
	SD		x.xx	x.xx
	Median		x.x	x.x
	Min, Max		xx, xx	xx, xx
etc	p-value*		0.xxxx	0.xxxx
				Tolperisone vs Cyclobenzaprine
				xx
				x.x
				x.xx
				x.x
				xx, xx

*Wilcoxon Signed Ranks test.

SAS Program Name:

Date:

Source Data: Listing 16.2.6.1.X

Table 14.2.12

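### The variance-components fallback in SAP 6.5.1 names no subject effect; read literally it ignores the crossover pairing and, if used, gives intervals that are too wide

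*SAP*

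**What the plan says.** Protocol 13.6 specifies a mixed model "with fixed effects for sequence, period, and treatment, and a random effect for subject within sequence", with an unstructured covariance and Kenward-Roger degrees of freedom. It gives no fallback.

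SAP 6.5.1 describes the model as a "mixed model repeated measures with fixed effects for sequence, period, and treatment, with repeated observations for subjects". The random subject effect is gone. The footnote to the Table 14.2.1.1 shell repeats this form: "repeated assessments for subjects, unstructured covariance structure, and Kenward-Roger degrees of freedom". SAP 6.5.1 then adds the contingency: "In the event an unstructured covariance structure fails to converge, a variance components covariance structure will be assumed".

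Three other places fix what depends on this sentence:

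- SAP 6.1.1 bases the sample size on the assumption that the "within-subject standard deviation for SDLP is approximately 6 cm".
- SAP 6.1.4 says the cyclobenzaprine-placebo "comparison is necessary to validate the experiment as having the ability to detect effects".
- SAP 6.5.2 carries the same model to other outcomes: "Secondary endpoints of VAS, SDC, and driving performance endpoints will be evaluated and presented similarly". The list includes Excessive Ay and Total Collisions (Table 14.2.6).

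**The concern.** With an unstructured covariance, leaving out the random subject effect does no harm, because the covariance matrix already holds the correlation between a subject's periods. Under the fallback it does matter. A variance-components structure placed on the repeated observations is diagonal. With no random subject effect beside it, nothing in the model links the three periods of one subject. Treatment differences are then judged against between-subject plus within-subject variance, although the design and the sample size rely on within-subject variance alone. Kenward-Roger cannot restore a covariance that the model omits.

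At stake are a missed non-inferiority result for tolperisone and a missed cyclobenzaprine-placebo difference, without which SAP 6.1.4 does not regard the experiment as validated. If the authors meant variance components together with the protocol's random subject effect, nothing is lost, but the text does not say so. The choice between the readings would be made only after the planned model had failed on the data.

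**Working it through.** **Inputs.** 30 completers (SAP 4.2); 6 sequences, taken as 5 subjects each (SAP 4.5); 3 periods; SD 6 cm, true difference 0 and margin 4.4 cm (SAP 6.1.1); upper limit of a two-sided 95% interval (SAP 6.1.3, 6.1.4). One model per day, as the Day X table shell implies. The intraclass correlation (ICC) is not in the documents; 0.3, 0.5, 0.7 and 0.8 are assumed.

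**The plan's own figure (over 90% power).** Power = Φ(4.4/SE − 1.96).

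- Reading A, 6 cm is the within-subject SD: SE = 6√(2/30) = 1.55 cm; Φ(0.88) = 81% (about 80% with t, 56 df).
- Reading B, 6 cm is the SD of the paired difference: SE = 6/√30 = 1.10 cm; Φ(2.06) = 98%.

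Only B reaches the stated power. That is a separate matter, so both readings are carried forward.

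**SE under the literal fallback.** Let σw and σb be the within- and between-subject SDs, with σb² = σw²·ICC/(1−ICC). Without sequence effects the SE grows by 1/√(1−ICC). With them, the residual pools 56 within-subject df, with mean square σw², and 24 between-subject df, with mean square σw² + 3σb². Its expectation is (56σw² + 24(σw² + 3σb²))/80 = σw² + 0.9σb², so the factor is √(1 + 0.9·ICC/(1−ICC)). In this balanced design the treatment estimate itself does not change; only its stated precision does.

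Simulation, 20,000 trials per setting, independence model against a model with subject effects:

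| | Subject effects kept | ICC 0.3 | ICC 0.5 | ICC 0.7 | ICC 0.8 |
|---|---|---|---|---|---|
| 1/√(1−ICC) | 1 | 1.20 | 1.41 | 1.83 | 2.24 |
| Factor with sequence effects | 1 | 1.18 | 1.38 | 1.76 | 2.14 |
| A: mean SE (cm) | 1.54 | 1.82 | 2.12 | 2.71 | 3.30 |
| A: NI power, one day | 80% | 69% | 55% | 28% | 11% |
| A: NI error at 4.4 cm | 2.5% | 1.0% | 0.4% | 0.1% | <0.1% |
| B: mean SE (cm) | 1.09 | 1.29 | 1.50 | 1.92 | 2.33 |
| B: NI power, one day | 98% | 95% | 90% | 69% | 42% |

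Hand check, A at ICC 0.5: a separate run of 10,000 trials gave a mean half-width of 4.23 cm, and Φ((4.4 − 4.23)/1.55) = Φ(0.11) = 54%, against 55% simulated. Coverage of the nominal 95% interval in that run was 99.1%.

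**Assay sensitivity, reading A.** Power to detect a true cyclobenzaprine effect:

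| True effect | Subject effects kept | ICC 0.3 | ICC 0.5 | ICC 0.7 |
|---|---|---|---|---|
| 4.4 cm | 80% | 69% | 54% | 28% |
| 6 cm | 97% | 93% | 87% | 64% |
| 8 cm | 99.9% | 99.7% | 99% | 94% |

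**How often the fallback would be used.** By day, the unstructured matrix has 3×4/2 = 6 parameters. On SDLP-like normal data, 0 of 200 fits failed (approximate one-sided 95% upper bound 3/200 = 1.5%).

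Sparse counts differ, because a period with no events has zero variance. Counts were simulated as Poisson with gamma subject rates (shape 0.5), so ICC = 2m/(2m+1) for mean m per drive, and 1/√(1−ICC) = √(1+2m):

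| Assumed mean m | 0.05 | 0.1 | 0.2 | 0.5 |
|---|---|---|---|---|
| Unstructured fits failing (200 each) | 54% | 15% | 2.5% | 0% |
| ICC | 0.09 | 0.17 | 0.29 | 0.50 |
| SE inflation if fallback used | 5% | 10% | 18% | 41% |

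These fits used a purpose-written REML optimiser, not SAS. Failure meant all-zero data, a non-positive-definite solution or a non-zero gradient.

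**The case against.** The harmful reading may not be the intended one. The protocol has a random subject effect, and a single diagonal residual hardly deserves the plural name variance components. Dropping the random effect beside an unstructured matrix is ordinary practice and shows no intent to ignore subjects later. This is fair, but the text does not exclude the literal reading: the SAP omits the effect twice and never says that it returns.

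Likelihood and harm also run in opposite directions. For SDLP the loss could be large but the trigger was never seen. For sparse counts the trigger is plausible but the inflation is small: failure rate times inflation is 0.54×5% ≈ 2.7%, 0.15×10% = 1.5% and 0.025×18% ≈ 0.5%. Those endpoints are secondary, and collisions have a separate Wilcoxon analysis. The failure rates rest on invented count means and may not carry over to SAS. All of this stands and limits the priority of the point.

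The high ICCs may be pessimistic. Under A, ICC 0.7 and 0.8 imply between-subject SDs of 6√(0.7/0.3) = 9.2 cm and 6√(0.8/0.2) = 12 cm, while inclusion criterion 5 screens out subjects with high practice SDLP. The loss at ICC 0.5 is still material under A.

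Finally, the error is conservative, and SAP 6.1.1 expects cyclobenzaprine effects above 4.4 cm; at 6 cm, power stays at 87% at ICC 0.5 even under the fallback. This too is correct, but a conservative error can still cost the trial a result that its data support.

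**Conclusion.** The concern holds on its conditional terms. As written, the fallback permits an analysis that ignores within-subject correlation in a crossover. If used, it inflates the SE by roughly 1.2 to 2.1 times for ICC 0.3 to 0.8. Per-day non-inferiority power falls from 80% to between 69% and 11% (reading A), or from 98% to between 95% and 42% (reading B).

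This rests on the literal reading, on positive within-subject correlation of assumed size, and on separate models by day. The first-choice analysis is unaffected, as are the paired tests: McNemar for SDLP and readiness, Wilcoxon for collisions. The chance of use is low for SDLP and appreciable only for rare-event secondary endpoints. The point should be corrected because two readings of one sentence give materially different primary results. It does not threaten the validity of a non-inferiority claim. Confidence is medium, because the intended model and the ICC are unknown.

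**What to change.** Replace the fallback sentence in SAP 6.5.1 with, for example: *If the unstructured covariance fails to converge, compound symmetry across a subject's periods will be used, with Kenward-Roger degrees of freedom.* The protocol's random effect for subject within sequence is an equally acceptable choice. The SAP should name one of the two, since they differ when the estimated correlation is negative. Carry the same wording into the Table 14.2.1.1 footnote, so that it also governs the secondary endpoints analysed with this model.

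The cost is one sentence and a footnote, with no new data. Compound symmetry assumes equal variances and equal correlations across periods. That is less restrictive than the present fallback, which assumes equal variances and zero correlation.
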